### Stage II/ III Disease Cohort:

Blood samples will be obtained on participants following signed informed consent. For patients in the high-risk stage II/III cohort, a blood draw will be performed 4-8 weeks after the completion of surgical management at the time of standard of care blood work. In participants who sign informed consent prior to definite surgical management, a pre-operative blood draw may be obtained at the time that standard of care pre-op blood work is performed. Blood samples will then be obtained every three months following the initiation of either adjuvant therapy or routine, close follow-up for up to two years.

**Pre-op consent:** Pre-op blood draw, 4-8 week post-op blood draw, then every 3 month blood draw following initiation of adjuvant therapy/ observation for up to 2 years.

**No pre-op consent:** 4-8 week post-op blood draw, then every 3 month blood draw following initiation of adjuvant therapy/observation for up to 2 years.

Of note, retrospective samples will be analyzed in participants who have previously signed informed consent to the melanoma tissue banking protocols, DFHCC study 02-017 and 11-181. These participants will not need to sign the consent form accompanying this protocol.

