### Prognostic Ability of the Assay

Baseline assay results will be categorized as positive or negative and also be described on a continuous scale. The proportion of patients with a positive baseline assay will be presented with a 90% exact binomial confidence interval. Based on a cohort size of 50, the confidence interval will be no wider than 0.25. Confidence intervals will also be presented for the subgroups of patients with intermediate- or high-risk disease. We will also summarize continuous baseline assay levels using descriptive statistics for the complete cohort and according to subgroups.

Preliminary assessments of prognostic ability will be conducted using Kaplan-Meier (K-M) product-limit estimates for relapse or survival and stratified log-rank tests. K-M estimates will be stratified by AJCC stage and assay results to explore assay performance across different prognostic groups. Relapse-free survival and overall survival estimates at pre-specified time points will be presented with 90% confidence intervals estimated using log(-log(survival)) methodology. A secondary analysis will be conducted in the cohort with blood- and tissue-based assessments according to the four groups defined by their combined positive/negative status to look for differences in prognosis.

The relative effect of the blood-based assay with respect to relapse or survival will be estimated using Cox regression models. Since the AJCC staging incorporates prognostic factors such as number of involved nodes, tumor burden, ulceration, and tumor thickness, the Cox models will be stratified by AJCC stage to allow for differences in the baseline hazard of relapse or death. Models will include as covariates age, site of the primary melanoma, sex, and baseline serum LDH in addition to the blood-assay results. We will use aggregated data for the primary models; secondary models will be fit separately for the intermediate- and higher-risk cohorts. Hazard ratios for the assay will be presented with 90% confidence intervals.

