### Predictive Ability of the Assay

The behavior of the blood-based assay over time will be summarized graphically by AJCC stage or according to melanoma treatment. The status of the assay will be shown at each assessment time for each patient, in addition to time of disease progression. Of particular note will be assessment times where a previously undetectable assay becomes detectable, or times where there is a doubling in the assay relative to baseline. Treatment will be classified into four groups: immunotherapy, BRAF/MEK inhibitors, other translational signal transduction/targeted therapies, or chemotherapy (cytotoxic therapy).

The first assessment of assay performance over time will take place at 3 months and will be based on fold-changes in the quantified assay relative to baseline. This early look will minimize the number of patients lost due to rapid progression of disease. Based on 18-month progression rates reported in the literature, we estimate that approximately 11% of patients will have progressed by the time of the 3-month assessment. For an initial cohort size of 50 patients, and assuming that 45 patients will have 3-month assay, a Wilcoxon-signed-rank test, comparing the observed fold-change with one, with a two-sided type-I error of 10%, will have 80% power to detect a difference in fold-change that is 0.41 times the standard deviation.

In more exploratory analyses, we will model the behavior of the assay over time using repeated measures, random-effects regression with the continuous assay measure as the dependent variable. Models will include as covariates AJCC stage and treatment classification, in addition to other prognostic factors. To investigate the relationship between the assay and PFS (or OS), we will use the extended Cox (EC) model with assay performance as the time-dependent covariate. Models will be stratified by AJCC stage, and will include treatment group and prognostic factors as predictors. In separate EC models, the assay will be modeled (a) on a continuous scale, (b) based on fold-changes from baseline, and (c) based on an indicator of assay response (double the baseline level or change from non-detectable to detectable).

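### Extended Cox model (c) for assay change names no adjustment for baseline assay status, so its hazard ratio can be confounded in either direction

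*Combined protocol and SAP*

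**What the plan says.** Section 9.1, Secondary Objective 2, Predictive Ability of the Assay, introduces the longitudinal work as exploratory: "In more exploratory analyses, we will model the behavior of the assay over time". It then turns to the relation between the assay and PFS or OS: "In separate EC models, the assay will be modeled (a) on a continuous scale, (b) based on fold-changes from baseline", with model (c) "based on an indicator of assay response (double the baseline level or change from non-detectable to detectable".

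The adjustment is given in one sentence: "Models will be stratified by AJCC stage, and will include treatment group and prognostic factors as predictors". The prognostic factors are not listed there. The only itemised list is under Prognostic Ability of the Assay, for the baseline Cox models: "Models will include as covariates age, site of the primary melanoma, sex, and baseline serum LDH in addition to the blood-assay results". In those models the baseline assay is the exposure, not an adjuster.

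The baseline result will be available in both forms: "Baseline assay results will be categorized as positive or negative and also be described on a continuous scale". Follow-up sampling is quarterly: "Blood samples will then be obtained every three months following the initiation of either adjuvant therapy or routine, close follow-up for up to two years".

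Section 2.3 (Rationale) gives two views of baseline detectability. Its closing paragraph aims to link the test with worse outcome after resection. Its third argument calls it uncertain whether detectable or high circulating BRAF is prognostic.

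**The concern.** Model (c) gives the value 0 to three kinds of patient: those never detectable, those detectable at baseline and stable, and those detectable at baseline and falling. If detectability after surgery carries risk, this comparison group mixes low-risk and high-risk patients. The value 1 also covers two events that arise from different starting points. Conversion can happen only to a patient who was non-detectable at baseline. Doubling has a meaning only for a patient who was detectable.

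Baseline status therefore determines which event a patient can have, and it may also affect relapse. That makes it a confounder of the indicator. A real signal from conversion could be diluted. A doubling signal could appear only because doublers are, by definition, patients who were positive at baseline. These are the events that the section singles out as of particular note, so the reading of (c) matters even in an exploratory analysis.

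**Working it through.** **Nearest stated figure.** The documents give no hazard ratio, event count or power for the extended Cox models. The only figure close by concerns the 3-month signed-rank test with 45 patients: "with a two-sided type-I error of 10%, will have 80% power to detect a difference in fold-change that is 0.41 times the standard deviation". It reproduces. Multiplying n by the minimum asymptotic relative efficiency of the Wilcoxon test gives 45 × 0.864 = 38.9 effective patients, and noncentral-t power then gives a detectable effect of 0.406 SD. It has no bearing on the point here.

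**Inputs for the check (all assumed; the documents give none).**
- p = share detectable at baseline, 0.30
- H = hazard ratio, detectable against never detectable, 3
- D = extra hazard ratio for doubling, 1.5
- never-detectable relapse hazard 3% per quarter and conversion 5% per quarter
- doubling 0, 5% or 20% per quarter
- quarterly visits for two years, as in Section 5.1

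**By hand, using the starting mix of patients.** Relative to a never-detectable patient, the average hazard in the value-0 group is (1 − p) + pH = 0.7 + 0.3 × 3 = 1.6.

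| Event | Against the mixed group | Against patients with the same baseline status |
|---|---|---|
| Conversion | H / 1.6 = 3 / 1.6 = 1.88 | 3 / 1 = 3.0 |
| Doubling | HD / 1.6 = 4.5 / 1.6 = 2.81 | 4.5 / 3 = 1.5 |

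Without baseline status, conversion is understated and doubling is overstated. The single coefficient of (c) averages the two, so its bias depends on the event mix.

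**By large-sample simulation with the same inputs.** The hand figures ignore later changes in the value-0 group; the simulation allows for them.

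| Doubling per quarter | HR for (c), unadjusted | HR for (c), with baseline status |
|---|---|---|
| None | 1.92 | about 3.0 |
| 5% | 2.26 | 2.25 |
| 20% | 2.89 | 2.08 |

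With conversions only, the unadjusted value is 2.56 when 10% are detectable at baseline and 1.53 when 50% are. The hand formula gives 3 / 1.2 = 2.5 and 3 / 2.0 = 1.5.

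**Other assumed values** (never-detectable hazard 0.02 per month, H = 2).
- Conversions only (5% per visit), unadjusted: 1.84, 1.56, 1.35 and 1.19 with 10%, 30%, 50% and 70% detectable at baseline. Adjusted: 2.0 throughout.
- 30% detectable, conversion 2% and doubling 20% per visit, no true doubling effect: 1.79 unadjusted, 1.28 adjusted.
- 30% detectable, conversion and doubling each 5% per visit, D = 1.5: 1.81 both ways. Entered as separate but unadjusted terms, conversion is 1.62 (true 2.0) and doubling is 2.41 (true 1.5).
- H = 1 (baseline not prognostic), conversions only: 0.99 both ways.

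The third case shows that adding baseline status to one combined indicator is not enough: 1.81 still averages 2.0 and 1.5.

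**Model (b).** Fold-change is continuous as written, with no categories, so there is no reference group. A patient stable at a low level and one stable at a high level both have fold-change 1. A fold-change from a non-detectable baseline is undefined unless a value is assigned, and no rule is given.

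**The case against.** The strongest reply is that the models are labelled exploratory, that no sample size or decision rests on them, and that the rest of the plan covers much of the ground. Model (a) uses the current level and does separate a stable-detectable patient from a never-detectable one. The Kaplan-Meier, log-rank and Cox analyses under Prognostic Ability estimate the effect of baseline status directly. This stands and limits the weight of the point. It does not repair (b) and (c), which are fitted as separate models.

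It can also be said that the unlisted prognostic factors could include the baseline assay. That is fair. A reader might infer that the plan rules out the adjustment, but the text shows only that it is not specified.

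A reader might further infer that the hazard ratio is always pulled towards 1. That follows only if conversions dominate. The definition of (c) includes doubling, which pushes the other way.

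Nor is a loss of power established. In simulations of 50 patients with conversions only (30% detectable, hazard ratio 4, conversion 8% and base hazard 5% per quarter), adjustment raised power at the two-sided 10% level from about 60% to 83%. Adding 8% doubling per quarter (extra hazard ratio 1.5) made it about 72% and 71%. With hazard ratio 3, base hazard 3%, conversion 5% and doubling 10% per quarter, power fell from about 53% to 39% after adjustment.

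**Conclusion.** The point holds for model (c) in this form: baseline assay status is not specified as a covariate, stable-detectable and never-detectable patients share the value 0, and two different events share the value 1. If baseline detectability is prognostic, the hazard ratio is confounded by baseline status. With 30% detectable and a hazard ratio of 3, the effect ranges from understatement (1.9 against 3.0) through no net difference to overstatement (2.9 against 2.1) as doubling goes from none to 20% per quarter.

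These sizes rest wholly on assumed inputs. The direction cannot be predicted from the documents, which give no conversion rate, doubling rate or baseline positivity. If baseline status is not prognostic, this confounding disappears, although the combined indicator would still average conversion and doubling.

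A reader might extend the reference-group argument to model (b). The text does not support that; the weakness in (b) is that it ignores the level at which a patient is stable. Model (a) is not affected.

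**What to change.** In extended Cox models (b) and (c), name baseline assay status (detectable yes/no, or baseline level) as a fixed covariate or a stratum. In (c), replace the combined indicator with two time-dependent terms, one for conversion and one for doubling. With baseline status in the model, converters are then compared with never-detectable patients and doublers with other patients detectable at baseline. For (b), state the value assigned to a non-detectable baseline. List the prognostic factors meant for these models.

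No new data are needed, because the baseline assay is already planned in binary and continuous form. As fixed covariates, the cost is one extra parameter in (b) and two in (c). Using baseline status as a stratum saves a parameter but thins the AJCC strata further. In a cohort of about 50 this will widen some intervals, and the change should be justified by interpretability, not by power.

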### Characteristics of Study Sample

Patient demographic and disease characteristics will be presented in the aggregate and by cohort. Characteristics measured on a continuous scale, such as age, will be summarized using N, mean, standard deviation, median and range. Categorical characteristics will be summarized using N and percentage.

## **10. PUBLICATION PLAN**

The results should be made public within 24 months of reaching the end of the study. The end of the study is the time point at which the last data items are to be reported, or after the outcome data are sufficiently mature for analysis, as defined in the section on Sample Size, Accrual Rate and Study Duration. If a report is planned to be published in a peer-reviewed journal, then that initial release may be an abstract that meets the requirements of the International Committee of Medical Journal Editors. A full report of the outcomes should be made public no later than three (3) years after the end of the study.

